Date of first enrollment	November 1, 2022
Target sample size	90
Recruitment status	Not yet started
Primary outcome(s)	
1) Difference in proportion of relapse-free weeks (time-frame; 12 months)
 
2) Difference in incidence rates of opioid-related healthcare utilization (time-frame; 12 months)

Key secondary outcome(s)	
1) Difference in Medication Satisfaction Questionnaire scores
 
2) Difference in World Health Organization Quality of Life – BREF Questionnaire scores
 
3) Difference in proportion of patients who attend <math>\geq 80\%</math> of scheduled clinic visits
 
4) Difference in opioid-related mortality proportions

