## 8 Design

The **STOP-IT** trial is designed as a pragmatic, multi-centre, randomised, controlled, open-label, superiority study with two parallel groups and primary endpoints of opioid positivity and healthcare utilization at 12 months after enrollment. Randomization will be performed with a 1:1 allocation ratio using a stratified, permuted-block group schema according to the following strata (no fixed ratio):

- 1) RAAM clinic site (Barrie, Orillia, Midland, Wasaga Beach)
- 2) Severity of OUD according to DSM-V criteria (moderate vs severe)

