#### 18.11 Routinely collected data

##### *18.11a Prior to induction*

For all RAAM clinic patients with OUD who are eligible to receive any opiate substitution therapy, the following demographic and baseline clinical and laboratory data are collected **prior to induction** with any treatment (Table):

Data	Description	Data type
Demographics		
Date of birth	Month/day/year	Mm/dd/yyyy
Sex at birth	Male: Female	Categorical
Pregnant	Yes: No	Categorical
Ontario health insurance plan number	Unique provincial insurance number assigned to every resident	xxxx-xxx-xxx-version code
Ontario drug plan status	Insured versus non-insured	Categorical
Residency	Homeless; transient (< 6 months at same address, couch surfing or shelter); stable (≥ 6 months at same address)	Categorical
Children in home	Yes: No	Categorical
Children ages	Years	Continuous
Telephone contact	Yes: No	Categorical
Number		(xxx)-xxx-xxxx
Employment status 	Full-time (≥ 40 hours per week for ≥ 90 days per year); Part-time (≤ 40 hours per week or ≥ 90 days per year); Casual (≤ 90 days per year); unemployed	Categorical
Incarceration 	Incarceration in ≤ 12 months (Yes: No)	Categorical
Race 	White: Non-white, non-indigenous: Indigenous	Categorical
Clinical		
OUD diagnostic screen	≥ 2 of 11 DSM-V criteria must be present ≤ 12 months for diagnosis of OUD	Categorical: range 0 to 11:
OUD severity	DSM-V criteria of mild, moderate or severe OUD	Categorical: mild (2-3 criteria); moderate (4-5 criteria); severe (≥6 criteria)
Medical history	Comorbid illness screen, including mental health and substance use	Categorical
Medications	Prescribed	Categorical

Alcohol use	Yes: No	Categorical
Opioid use	Type: Route	Categorical
Other substance use	Type: Route	
Recent substance/opioid use	Timeline Followback questionnaire (assesses use and frequency of use of substances over the previous 7 days)	Categorical
Hospitalization	Substance-related $\leq$ 12 months (includes emergency room visit, admission to hospital, mental health or detoxification facility) (Yes: No)	Categorical
General physical exam	Vital signs; height; weight	Continuous
Opioid withdrawal screen	$\geq$ 3 of the following: dysphoria; nausea or vomiting; muscle aches; lacrimation or rhinorrhea; pupillary dilation or piloerection or sweating; diarrhea; fever; insomnia; yawning	Categorical; range 0-9
Jaundice	Yes: No	Categorical
Mental status	Glasgow coma scale	Categorical (range 3-15)

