## 20.11 Primary

### 20.11a Opioid positivity

We will use a 3-level hierarchical design to model the relapse-free weeks data where the observation for each week (Level 1) will be coded as binary; relapse-free week if urine drug screen and self-report is negative for non-prescribed opioid use, and otherwise relapse week if either is positive for non-prescribed opioid use. As described in Section 12.11, imputation of missing data will occur for those weeks in which a urine drug screen/self-report was not scheduled according to the results of the subsequent week's urine drug screen/self-report. Level 1 observations are clustered within individual participants (Level 2), which are nested within RAAM clinic sites (Level 3). We will analyse the outcome data using multi-level, mixed-effects logistic regression analysis with random effects estimated for the variance in the intercepts of both participant and clinic levels. The model will also include a random slope on the indicator for OUD severity (moderate versus severe) in the Level 2 random effects equation using an unstructured covariance structure between intercept and slope. We will also include clinic visit (week) and an interaction term between clinic visit and treatment. A sensitivity analysis will be conducted to compare this baseline model with an extended model that includes any baseline demographic or clinical variables that appear to be unbalanced at Level 1. The models will be compared using the likelihood-ratio comparison test for superiority. Post-regression analyses using *margins* command will be used to estimate difference in proportions of RFWs between treatment groups.

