### 20.11b Healthcare utilization

We will model the days of healthcare utilization as count data, with the period of follow-up while alive during the study period as the exposure period. We will analyse the data using a Poisson regression model. We will include an indicator for OUD severity. We will include any baseline demographic or clinical variables that are unbalanced at Level 1.

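### The primary healthcare-utilization model picks covariates by observed baseline imbalance and pre-specifies neither clinic nor prior-year hospitalization

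*Combined protocol and SAP*

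**What the plan says.** Section 1.1 lists two primary outcomes, the second being "Difference in incidence rates of opioid-related healthcare utilization (time-frame; 12 months". For that outcome section 20.11b says "We will analyse the data using a Poisson regression model", then "We will include an indicator for OUD severity", and then "We will include any baseline demographic or clinical variables that are unbalanced at Level 1". It names no other covariate and no clinic term.

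Elsewhere in the same document:
- Section 8 stratifies randomization by "RAAM clinic site (Barrie, Orillia, Midland, Wasaga Beach" and by OUD severity; section 16.1 repeats both factors.
- Sections 20.11a and 20.12 give clinic a random intercept.
- Section 20.11a defines Level 1 as the weekly observation and Level 2 as the participant. There the imbalance rule belongs to a secondary step: "A sensitivity analysis will be conducted to compare this baseline model with an extended model". The second of these two models is described as one "that includes any baseline demographic or clinical variables that appear to be unbalanced at Level 1".
- Section 20.12 puts the imbalance rule into the main repeated-measures models for satisfaction and quality of life.
- Section 17 states that data analysts are not masked.
- Section 18.11a collects, before induction, a yes/no item on substance-related hospitalization in the past 12 months, which "includes emergency room visit, admission to hospital, mental health or detoxification facility".

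**The concern.** The stated method for a primary analysis selects covariates on chance imbalance rather than on prognosis. It also leaves open what counts as unbalanced, which variables are candidates and who decides. Analysts who can see the data by arm would settle these questions after the fact.

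The rule is also badly defined. Baseline variables belong to participants, which is Level 2 in section 20.11a, and section 20.11b sets up no levels at all.

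Two terms with a good claim to inclusion are left to this rule. Clinic is balanced by design, so an imbalance screen would rarely admit it. Prior-year hospitalization or emergency use is the closest baseline analogue of the outcome, and it enters only by accident. At stake are the credibility of a primary estimate and some precision.

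**Working it through.** **The plan's own figure.** The plan gives no figure for covariate selection. Its utilization power statement (sections 14.3 and 14.4) is 99% for 2 versus 1 healthcare days per 1,000 patient-days with 3,650 patient-days per group. Expected counts are 7.3 and 3.65; z = 3.65/√(7.3 + 3.65) = 1.10; power = Φ(1.10 − 1.96) ≈ 0.20. The 99% does not reproduce. That is a separate matter, and nothing below relies on it.

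**How many variables an imbalance rule admits.** Inputs: 45 per arm (section 14.4), and about 20 usable candidates. The 20 is an approximate count from section 18.11a, leaving out identifiers, telephone entries, pregnancy (an exclusion) and severity (already in the model).
- Under randomization a standardized mean difference (SMD) has standard deviation √(2/45) = 0.211, so P(|SMD| > c) = 2[1 − Φ(c/0.211)].
- c = 0.1: 0.64 per variable, about 12.7 of 20.
- c = 0.2: 0.34 per variable, about 6.9 of 20.
- c = 0.25: 0.24 per variable, about 4.7 of 20.
- A p < 0.05 screen: 20 × 0.05 = 1.0 expected; P(at least one) = 1 − 0.95^20 = 0.64. If correlation leaves only 10 effectively independent items, 1 − 0.95^10 = 0.40.

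**Set against the information available.** With full follow-up, 45 × 365 = 16,425 patient-days per arm. At 2 and 1 per 1,000 that is 32.9 + 16.4 ≈ 49 healthcare days in the whole trial. Counting treatment, severity and the admitted variables at one parameter each:
- p < 0.05 screen: 49/3 ≈ 16 events per parameter.
- SMD 0.2: 49/8.9 ≈ 5.5.
- SMD 0.1: 49/14.7 ≈ 3.3.

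The unstated threshold largely decides the model.

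**Simulation of the 20.11b model.** 90 patients, 4 clinics, stratified blocks of 6, 3,000 runs per scenario, no extra overdispersion. Clinic and prior-hospitalization effects are assumptions, because the documents give none.

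Power at a true rate ratio of 0.5, robust standard errors:

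| Covariates | Clinic RR up to 2, hospitalization RR 3 | Clinic RR up to 1.5, hospitalization RR 2 |
|---|---|---|
| Severity only | 0.55 | 0.60 |
| Severity + clinic | 0.57 | 0.60 |
| Severity + clinic + prior hospitalization | 0.63 | 0.62 |
| Imbalance-picked (SMD 0.1, 0.2, 0.3) | 0.54–0.55 | 0.57 |

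Type I error under the null, over three sets of covariate effects including none:
- One fixed imbalance rule: 0.041–0.056 with robust standard errors. With model-based errors it is 0.048–0.066, against 0.046–0.083 for severity only, so the excess there comes from omitted predictors, not from the picking.
- Most favourable of four rules (no picking, SMD 0.1, 0.2, 0.3): 0.076–0.083 robust, 0.069–0.117 model-based.

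At a true rate ratio of 0.5, the four rules disagreed on significance in 16–20% of trials.

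**The case against.** Much can be said for the plan, and several stronger readings that a reader might infer do not hold.

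- *The rule governs both primary analyses.* It does not. In section 20.11a it shapes only a sensitivity model. What stays open there is which model is reported if the likelihood-ratio comparison favours the extended one.
- *The analysis ignores the stratification.* Only clinic is missing, and only from the utilization model. Severity is named in 20.11b, and clinic is a random intercept in 20.11a and 20.12.
- *Prior hospitalization is excluded.* It is not barred; it is not pre-specified. Nor do the documents say that it predicts utilization. The factors that section 18.11a calls risk factors are employment, incarceration and race. The item is yes/no for any substance, while the outcome counts opioid-related days. Calling it the closest analogue is a judgement, though a reasonable one.
- *Selecting on imbalance inflates type I error.* One fixed rule did not do so in the simulation. Inflation appeared only when the most favourable of several rules was taken.
- *The chance of an accidental covariate is about 79%.* That is 1 − 0.95^30 and counts every listed row, including some that could not serve as covariates.
- *Adjustment is worth 11% to 25% more patients.* That is 1/(1 − R²) at an assumed R² of 0.1 to 0.2, a linear-model formula that does not carry over to this count model.
- *The Level 1 wording is meaningless.* In 20.11b the patient could be read as the lowest level. The term still conflicts with 20.11a and needs rewording.

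What survives is confined mainly to 20.11b: an undefined, data-dependent rule in a primary analysis, no clinic term, and a relevant collected covariate left to chance.

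**Conclusion.** The point holds for the primary healthcare-utilization analysis, and the plan should be changed. Confidence is high that the specification is inadequate. No threshold or candidate list exists, the analysts are unmasked, and the number of admitted variables could plausibly run from about 1 to about 13 (20 independent candidates assumed).

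Confidence is lower on precision. The power difference, 0.62–0.63 against 0.54–0.57, rests on assumed covariate effects, full follow-up and no overdispersion. Most of it comes from prior hospitalization: adding clinic alone moved power from 0.55 to 0.57 in one scenario and by less than 0.01 in the other. In the weaker-effects scenario the gain over severity alone is only 0.62 against 0.60. The case for clinic is therefore mainly consistency with the randomization and with the other models.

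**What to change.** - **20.11b:** pre-specify treatment, clinic site, OUD severity and prior-12-month substance-related hospitalization (yes/no). Delete the imbalance sentence from the primary model, and keep such adjustment as a labelled sensitivity analysis with a stated candidate list and threshold.
- **20.12:** move the imbalance rule out of the main repeated-measures models in the same way. Leave the unadjusted retention and mortality tests as they are.
- **20.11a:** keep the clinic random intercept, on which the three-level sample size rests. Add OUD severity (now described only as a random slope) and the week-0 urine and self-report result (scheduled in section 13) as fixed covariates. State that the baseline model is primary whatever the likelihood-ratio comparison shows.
- **All three:** describe baseline variables as participant-level and drop the Level 1 reference.

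The cost is SAP wording, since every variable is already collected. The downside is a few more parameters in a model with few events. Treatment, severity, three clinic contrasts and prior hospitalization make six, or 49/6 ≈ 8 expected healthcare days per parameter at the assumed rates with full follow-up. The SAP should therefore also say in advance what is done if a clinic records no healthcare days.

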## 20.12 Secondary outcomes

We will use a 3-level hierarchical design to model all the repeated measures outcomes (Medications Satisfaction Questionnaire and the WHOQOL-BREF) where the outcomes will be coded as continuous. Level 1 observations are clustered within individual participants (Level 2), which are nested within RAAM clinic sites (Level 3). We will analyse the data using multi-level, mixed-effects linear regression analysis with random effects estimated for the variance in the

intercepts of both participant and clinic levels. We will include a random slope on the indicator for OUD severity (moderate versus severe) in the Level 2 random effects equation using an unstructured covariance structure between intercept and slope. We will also include clinic visit and an interaction term between clinic visit and treatment, along with any baseline demographic or clinical variables that are unbalanced at Level 1.

Both clinic retention and mortality will be coded as binary outcomes. We will conduct unadjusted analyses for both using a chi-squared test (with continuity correction) or Fisher's exact test depending on cell sizes.

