### 12.22 Quality of life

Difference in the World Health Organization Quality of Life – BREF scores (WHOQOL-BREF). The 26-item questionnaire is a validated, self-report instrument that assesses 4 domains of quality of life: physical health (7 items), psychological health (6 items), social relationships (3 items) and environment (8 items). There are also 2 items that measure overall quality of life and general health. The questionnaire takes 15-20 minutes to complete. The questionnaire prefaces each item, “Think about your life in the last two weeks..”. The responses are on a 5-point Likert scale, ranging from 1=not at all/very dissatisfied/never/very poor to 5=very good/very satisfied/an extreme amount/extremely/completely/always, depending on the item. The questionnaire is valid, reproducible, relevant to both healthcare providers and patients with OUD, and has been shown to be responsive to changes in quality of life across cultures, geography and etiology.

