# 13 Participant timeline

			Study Period (Weeks)																											
			-1	0	T1	T2	T3	T4	T5	T6	T7	T8	T9	T10	T11	T12	T13	T14	T15	T16	T17	T18	T19	T20	T21	T22	T23	T24		
Activity	C R F	M R P	w-1	w0	w2	w4	w6	w8	w10	w12	w14	w16	w18	w20	w22	w24	w26	w28	w30	w32	w34	w36	w38	w40	w42	w44	w46	w48		
Enrollment																														
Expressed Consent	N	HCP	X																											
Eligibility Screen	Y	HCP SC	X																											
Informed Consent	N	HCP SC	X																											
Randomization	Y	SC		X																										
Demographics	Y	HCP		X																										
Pregnancy test	Y	HCP	X																											
EKG	Y	HCP	X																											
Bloodwork	Y	HCP	X																											
Interventions																														
Suboxone®	Y	HCP		X																										
Sublocade®	Y	HCP		X		X		X		X		X		X		X		X		X		X		X		X		X		
Counselling	Y	HCP		X	X	X	X	X		X		X		X		X		X		X		X		X		X		X		
RAAM clinic visit	Y	HCP		X	X	X	X	X		X		X		X		X		X		X		X		X		X		X		
Pre-clinic visit phone call	Y	HCP SC		X	X	X	X	X		X		X		X		X		X		X		X		X		X		X		
Assessments																														
General exam	Y	HCP		X	X	X	X	X	X	X	X	X	X	X	X	X	X	X	X	X	X	X	X	X	X	X	X	X	X	X
Urine drug test	Y	HCP	X	X	X	X	X	X	X	X	X	X	X	X	X	X	X	X	X	X	X	X	X	X	X	X	X	X	X	X
Timeline Followback	Y	HCP	X	X	X	X	X	X	X	X	X	X	X	X	X	X	X	X	X	X	X	X	X	X	X	X	X	X	X	X
MSQ	Y	HCP SC					X			X			X			X			X			X			X			X		
WHOQOL-BREF	Y	HCP SC		X						X						X						X								X
Pregnancy test	Y	HCP				X		X		X		X		X		X		X		X		X		X		X		X		
SAE	Y	HCP		X																										
EKG	Y	HCP																												
Bloodwork	Y	HCP																												

CRF=case report form; MRP=most responsible person; N=No; Y=Yes; HCP=healthcare provider; SC=study coordinator; EKG=electrocardiogram; MSQ=medication satisfaction questionnaire; WHOQOL-BREF=Quality of life questionnaire; SAE=severe adverse event

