#### 14.4 Final sample size

In a hierarchical 3-level mixed effects model with 45 and 45 level 2 units (RAAM clinic patients) randomized to Suboxone® and Sublocade® in a 1:1 ratio, 4 level 3 units (RAAM clinics) in total and an average of 5 level 1 units (RFWs) per level 2 unit, 90.0% power is achieved to detect a difference in RFWs proportions of at least 0.15, where the Suboxone® and Sublocade® RFWs proportions are 0.3 and 0.45, respectively, assuming that the correlation between level 1 units in a level 2 unit is 0.8 and the correlation between level 2 units in a level 3 unit is 0.025, and the 2-sided test is performed at the 5% significance level. Using even a much smaller sample size (N=20 patients per group with 50% loss-to-follow-up over 12-month study period), a 2-sided comparison of two incidence rates (number of healthcare days per 1000 patient days exposure) with a sample size of 3650 patient days exposure per group would achieve 99% power at the 0.05 significance level to detect a difference in incidence rates of at least 1 if the Suboxone® group incidence rate was 2.

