#### 18.12 Study-specific data

Data	Description	Data type
Medication Satisfaction Questionnaire	"How satisfied are you with your medication?"	Categorical: Range 1-7
WHOQOL-BREF	26-item questionnaire measuring quality of life in 4 domains: physical health;	Continuous: Each domain score standardized to scores 0 (worse) to 100 (best)

	psychological health; social; environment	
Hospitalization 	Any Royal Victoria Regional Health Centre emergency room visits, admissions to hospital or mental health or detoxification centre since previous clinic visit (Yes: No)	Categorical
Reason for visit/admission	Opioid-related (Yes: No)	Categorical
Serious adverse events 	Hospitalization (for any reason)	Categorical
Reason	Opioid-related (Yes: No)	Categorical

 Only hospitalization events associated with the Royal Victoria Regional Health Centre are accessible to the RAAM clinic healthcare providers as they clinics share the same electronic health record system as previously described. All other hospitalizations would have to be self-reported by the participants and consent for access to the health records would then need to be secured by the RAAM clinic healthcare providers.

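### The WHOQOL-BREF model does not pre-specify adjustment for the week-0 score or name its treatment contrast, so available precision may be lost

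*Combined protocol and SAP*

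**What the plan says.** - **Outcome.** Section 12.22 defines the endpoint as "Difference in the World Health Organization Quality of Life – BREF" scores, with no time point and no statement that it is a change from baseline. Section 18.12 treats the four domain scores, each on a 0 to 100 scale, as continuous.
- **Schedule.** The table in Section 13 marks the questionnaire at week 0 and again at weeks 12, 24, 36 and 48. The last mark is read as week 48, because the column alignment is disturbed at the end of the row.
- **Model.** Section 20.12 specifies "multi-level, mixed-effects linear regression analysis with random effects estimated for the variance in the" intercepts of participant and clinic, plus a random slope on OUD severity. It continues: "We will also include clinic visit and an interaction term between clinic visit and treatment, along with any baseline demographic or clinical variables". Baseline variables are admitted on one condition, that they are "baseline demographic or clinical variables that are unbalanced at Level 1".
- **Baseline set.** Section 18.11a introduces its table by saying that "the following demographic and baseline clinical and laboratory data are collected" before induction. The WHOQOL-BREF is not in that table. It is listed in Section 18.12 as study-specific data.
- **Contrast.** Section 20.11a names a post-estimation margins step for relapse-free weeks. Section 20.12 names none for quality of life.

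**The concern.** A patient's own starting score is usually a strong predictor of later scores on the same scale, and the trial already plans to collect it. The gain from adjusting for it comes from that correlation, not from whether the arms happen to differ at week 0. A rule that admits baseline variables only when they are unbalanced therefore does not secure the gain.

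The silence about week 0 leaves several analyses open. Week 0 may be dropped, kept as an outcome row with the arms free to differ there, or used as a covariate. With week 0 kept as a row, the reported effect could be a week-48 margin, a change from week 0, or an average over visits. These have different standard errors, and one has a different expected value. Section 17 states that the data analysts are not masked, so the choice should be fixed in writing beforehand. At stake is the precision and clarity of one key secondary outcome in a 90-patient trial.

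**Working it through.** The plan gives no power, SD, effect size or correlation for the WHOQOL-BREF, so it has no figure to reproduce. The check is a comparison of variances.

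**Inputs**
- Sample size from Section 14.4: "with 45 and 45 level 2 units (RAAM clinic patients) randomized" 1:1.
- One baseline and four follow-up scores (Section 13).
- Assumed: unit SD at each visit, the same correlation r between any two visits, complete data and the usual large-sample variance for covariate adjustment. Since r is not in the documents, 0.3 to 0.7 is shown.

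**Formulas.** The variance of the treatment difference is (2/45) × V. For the average of weeks 12 to 48:
- A, week 0 left out: V = (1 + 3r)/4
- B, change from week 0: V = (1 + 3r)/4 + 1 − 2r
- C, week 0 as covariate: V = (1 + 3r)/4 − r²

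Hence A − C = r² and B − C = (1 − r)². Both are positive for any r strictly between 0 and 1, so C is the most precise of the three. The factor 2/45 cancels in the ratios.

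| r | A | B | C | SE ratio C/A | Cut against A | SE ratio C/B | Cut against B |
|---|---|---|---|---|---|---|---|
| 0.3 | 0.475 | 0.875 | 0.385 | 0.900 | 10% | 0.663 | 34% |
| 0.5 | 0.625 | 0.625 | 0.375 | 0.775 | 23% | 0.775 | 23% |
| 0.6 | 0.700 | 0.500 | 0.340 | 0.697 | 30% | 0.825 | 18% |
| 0.7 | 0.775 | 0.375 | 0.285 | 0.606 | 39% | 0.872 | 13% |

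For example, at r = 0.6, C/A = √(0.340/0.700) = 0.697 and C/B = √(0.340/0.500) = 0.825.

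**Week 48 alone.** V is 1 with week 0 left out, 2(1 − r) for change and 1 − r² adjusted. At r = 0.5, 0.6 and 0.7, adjustment cuts the SE by 13%, 20% and 29% against leaving week 0 out, and by 13%, 11% and 8% against change. At r = 0.3 the cut against leaving it out is 5% (√0.91 = 0.954). If week 0 is an outcome row with the arms free there, the week-48 margin is still the unadjusted contrast (V = 1).

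**Averaging all five visits.** If week 0 is an outcome row and a constant effect δ starts after it, the five-visit average is (0 + 4δ)/5 = 0.8δ.

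**The case against.** The strongest reply is that the visit-by-treatment interaction already uses the baseline. If week 0 is an outcome row, the interaction terms measured from week 0 are change-from-baseline contrasts, which are neither diluted nor blind to the starting score. This stands as a possible reading, and it is why the working includes comparator B. On that reading the gain from adjustment gets smaller as r rises. Section 20.12 also lists no treatment main effect. Read literally, with week 0 as the reference visit, the model would hold the arms equal at week 0, which is one of the remedies proposed below. But the text states neither reading.

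A reader might infer that the planned quality-of-life effect is diluted to four fifths. The documents do not support that. It requires an equal average over all five visits, and no such contrast is stated.

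A reader might also infer that the model adjusts for nothing except unbalanced variables. That is not so: the clinic random intercept and the random slope on OUD severity are included unconditionally. What is missing is a fixed effect for severity, which is a stratification factor.

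Finally, adjustment is not free of difficulty here. Section 18.21 allows study questionnaires within 2 weeks either side of the scheduled date, with no exception for week 0. Under Section 11.1 the first study dose is given on Day 0, and the trial is open-label. A nominal week-0 score could therefore be taken after allocation and first dose, and conditioning on it could remove part of the treatment effect. Patients without a week-0 score would drop out of a simple covariate model. Both objections stand, and the fix has to meet them.

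**Conclusion.** The point holds as one of precision and incomplete specification, not of demonstrated bias. Section 20.12 does not commit to using the week-0 domain score and does not name the treatment contrast. The direction of the gain against comparators A and B follows for any r strictly between 0 and 1, under equal correlation. Its size depends on r and on which analysis would otherwise be run, and the documents settle neither. Equal correlation over 48 weeks is a further assumption.

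The point is confined to the WHOQOL-BREF. It does not extend to the Medication Satisfaction Questionnaire, which has no week-0 measurement.

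**What to change.** 1. Require the week-0 WHOQOL-BREF to be completed before randomisation, and exempt it from the plus or minus 2-week window.
2. In Section 20.12, enter the week-0 domain score as a fixed covariate whatever its balance, with weeks 12, 24, 36 and 48 as the outcomes. Alternatively, keep week 0 as an outcome row with the arm means constrained equal there, which retains patients whose week-0 score is missing.
3. Add OUD severity as a fixed effect. Clinic is already a random intercept and needs no change.
4. Name the average week 12 to 48 difference as the reported treatment effect for each domain.
5. State how missing or late week-0 scores will be handled.

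The cost is a few sentences in the SAP and a firmer baseline procedure at the clinics. No extra questionnaire is needed. The rule in item 5 is the one small burden.

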### 12.23 Clinic retention

Difference in proportion of patients who attend  $\geq 80\%$  of scheduled clinic visits, where a **clinic visit is defined as a scheduled visit with a RAAM clinic healthcare provider for any reason, including urine drug testing, medication administration, or counselling**. Clinic retention is the most commonly reported outcome measure in opioid substitution trials, with 46% reporting it as an outcome. However, there is no “gold standard” definition of retention, with over 16 different methodologies used to measure retention in 28 trials of opiate substitution therapy. The number of clinic visits any patient will be assigned will include those scheduled as part of the trial and any other visits scheduled at the discretion of the RAAM clinic healthcare providers. The measure of clinic retention used in this trial is valid, objective, reproducible, relevant to both healthcare providers and patients with OUD, and has been shown to be responsive to opiate substitution therapies in previous studies.

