## 16 Allocation

### 16.1 Sequence generation

Participants will be randomly assigned to either Suboxone® or Sublocade® with a 1:1 allocation schema as per a computer-generated randomisation schedule stratified by RAAM clinic site and severity of OUD (moderate versus severe by DSM-V criteria) using permuted blocks of size 6 in each strata. A single block size was chosen since the next block size of 18 might be too large to allocate patients in a 1:1 ratio in the smaller RAAM clinics. The block size will not be disclosed to ensure concealment. Sufficient numbers of blocks will be prepared *a priori* to ensure sufficient coverage for all strata in the event that they have different sample sizes as there will be no *a priori* fixed ratio for enrollment in the different strata.

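### Clinic retention is tested without the randomization strata and with a continuity correction that holds the error rate to at most 2.9% at 45 per arm, which costs power on a secondary outcome

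*Combined protocol and SAP*

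**What the plan says.** Section 12.23 defines retention as "Difference in proportion of patients who attend" at least 80% of their scheduled visits. Section 20.12 adds that "Both clinic retention and mortality will be coded as binary outcomes", and then: "We will conduct unadjusted analyses for both using a chi-squared test (with continuity correction"), with Fisher's exact test as the alternative according to cell sizes. It names no confidence interval, and no method for one, for the difference in retention.

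Section 8 lists the randomization strata as clinic site and "Severity of OUD according to DSM-V criteria (moderate vs severe"). Section 16.1 confirms a schedule "stratified by RAAM clinic site and severity of OUD (moderate versus severe by DSM-V criteria) using permuted blocks of size 6 in each strata".

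The other modelled outcomes do use these factors. Severity enters the relapse-free-week model (20.11a), the healthcare-utilization model (20.11b) and the satisfaction and quality-of-life models (20.12). The multilevel models also carry clinic as a random effect.

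**The concern.** Two choices in one sentence of the plan each reduce sensitivity. The continuity correction pulls the chi-squared statistic towards zero, so the test rejects less often than its nominal level allows. Leaving out the stratification factors adds to this: stratified blocks balance the arms on clinic and severity, but an unstratified test still counts variation between strata as noise. If either factor predicts attendance, the test becomes still more conservative.

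At stake is power for a secondary comparison in a trial of 90 patients. The analysis also lacks a stated interval for the difference that Section 12.23 makes the outcome.

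**Working it through.** **Inputs from the documents.** Arm sizes: "45 and 45 level 2 units (RAAM clinic patients) randomized to Suboxone" and Sublocade (Section 14.4). Level: "the 2-sided test is performed at the 5% significance level" (Section 14.4), stated for the primary outcomes and assumed here to apply to retention. Strata: 4 clinics × 2 severity levels = 8, in blocks of 6 (Section 16.1). Analysis is by allocation (Section 20.1), so the planned table is 45 v 45.

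**Assumptions.** Retention rates, the odds ratio and the stratum effects. The documents give none of these, so ranges are shown.

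**1. The plan's own two-proportion figure.** Section 14.2 gives 160 per group for 0.30 v 0.45 with an unpooled Z-test at 80% power. The formula is n = (p₁q₁ + p₂q₂)(z₀.₉₇₅ + z₀.₈₀)²/d² = (0.21 + 0.2475)(1.960 + 0.842)²/0.15² = 159.6, which rounds up to 160. The figure reproduces. It concerns relapse-free weeks; no power or expected rate is stated for retention.

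**2. The statistic.** With a, b (retained, not retained) in one arm and c, d in the other, the corrected statistic is N(|ad − bc| − N/2)²/[(a+b)(c+d)(a+c)(b+d)], and the test rejects above 3.841. The uncorrected form drops N/2. For 18/45 v 28/45, |ad − bc| = |18×17 − 27×28| = 450 and the denominator is 45×45×46×44 = 4,098,600.
- Uncorrected: 90×450²/4,098,600 = 4.45, which rejects.
- Corrected: 90×405²/4,098,600 = 3.60, which does not.

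**3. Exact size at 45 v 45.** For a common retention rate p, sum the product of the two binomial(45, p) probabilities over every table that rejects.

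| Common rate | Corrected | Uncorrected |
|---|---|---|
| 0.1 or 0.9 | 1.6% | 5.9% |
| 0.2 or 0.8 | 2.5% | 5.4% |
| 0.3 or 0.7 | 2.9% | 5.35% |
| 0.4 or 0.6 | 2.7% | 4.9% |
| 0.5 | 2.65% | 4.5% |
| Maximum over all rates | 2.93% (at 0.67) | 6.0% (near 0.08 or 0.92) |

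Switching to Fisher's test when a cell is below 5 (expected or observed) leaves the maximum at 2.93%. Fisher's test alone peaks at 3.16%. At other arm sizes the corrected test peaks at 3.1% (42 v 48), 3.1% (44 v 44) and 3.75% (42 v 42).

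**4. Exact power at 45 v 45, assumed rates.**

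| Retention rates | Corrected | Uncorrected | Loss (points) |
|---|---|---|---|
| 0.40 v 0.65 | 57.0% | 65.4% | 8.4 |
| 0.40 v 0.70 | 75.3% | 81.8% | 6.5 |
| 0.50 v 0.70 | 39.5% | 48.9% | 9.4 |

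**5. Effect of the strata, by simulation.** Eight strata, blocks of 6, N = 90; 8,000 null and 3,000 alternative replicates per setting. Power is for an assumed odds ratio of 3 and control rate of 0.5. Moderate effects are a clinic SD of 0.5 and a severity effect of 0.5 on the logit scale; strong effects are 1 and 1. CMH is the Cochran-Mantel-Haenszel test stratified by clinic and severity, without correction.

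| Stratum effects | Planned corrected test | Uncorrected, unstratified | CMH |
|---|---|---|---|
| None | 62% | 69% | 68% |
| Moderate | 58% | 66% | 69% |
| Strong | 43% | 53% | 62% |

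The size of the planned test falls to about 2.3% with moderate effects and 1.4% to 1.7% with strong ones. CMH held 4.4% to 5.2% in these settings, and 4.3% to 5.5% in a further simulation that included retention near 0.9. The Monte Carlo standard error is about √(0.05×0.95/8000) = 0.24 points for size and √(0.5×0.5/3000) = 0.9 points for power.

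**The case against.** The strongest defence is that a conservative, unadjusted test of a secondary binary outcome is legitimate. It adds no false positives, touches neither primary conclusion, and no power is claimed for retention. All of this is correct, and it limits how much the point matters. It does not make the choice a matter of taste: the stratified test had more power than the planned one in every setting tried and kept its size near 5%.

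Several stronger readings are tempting, and the documents do not support them:

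- **That the correction can be dropped at no cost.** It buys a guarantee. The plain uncorrected test reaches 6.0% at extreme rates for 45 v 45, and with no expected retention rate in the documents such rates cannot be excluded.
- **That the error rate is always under 3%.** This holds at 45 v 45. Blocks of 6 in 8 strata with no fixed enrolment ratio do not guarantee that split, and nearby sizes can go up to 3.75%.
- **That the strata are known to predict attendance.** Nothing in the documents shows it. The clinics share an owner, manager and medical lead (Section 15). With no stratum effect, step 5 shows essentially all of the gain coming from dropping the correction.
- **That small samples are unprovided for.** Fisher's test is already in the plan for small cells, so keeping it for mortality restates what is there.
- **That no effect measure is specified.** Section 12.23 defines one, the difference in proportions. Only its interval and method are missing.

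**Conclusion.** The point holds as a worthwhile improvement to a secondary analysis. The planned retention test is valid but conservative, with an exact size of at most 2.9% at 45 v 45, and it leaves out factors that the trial randomizes by and uses in its other models. The correction alone costs about 6 to 9 points of power in the three scenarios of step 4. Against a stratified uncorrected test the loss in step 5 is about 6 points with no stratum effect, 11 with moderate effects and 19 with strong ones.

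These figures rest on a two-sided 5% level carried over from the primary outcomes, on arms at or near 45 each, and on assumed retention rates, odds ratio and stratum effects. A reader might infer that the retention result would be invalid or the trial's main conclusions weakened. Neither follows: the error is on the cautious side and is confined to this outcome.

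**What to change.** In Section 20.12, separate retention from mortality.

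- **Retention:** analyse stratified by clinic and OUD severity without continuity correction. Either use the Cochran-Mantel-Haenszel test with a Mantel-Haenszel risk difference and 95% confidence interval, or logistic regression adjusted for both factors followed by *margins*, the command already planned for relapse-free weeks in Section 20.11a. State the significance level.
- **Sparse strata:** specify in advance how they are collapsed. The average is 90/8, about 11 patients per stratum, and enrolment by clinic is not fixed.
- **Mortality:** keep Fisher's exact test, since few events are likely.

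No extra patients or data are needed. The price is that the retention test is no longer guaranteed conservative: its actual size may slightly exceed 5% at some rates (4.3% to 5.5% in simulation). Because Section 17 leaves the analysts unmasked, the change should be made before outcome data are examined.
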